3.2 Basic Design Characteristics

Up to 44 patients with locally advanced or metastatic pancreatic neuroendocrine tumors who meet eligibility criteria will be enrolled sequentially into three cohorts.

3.2.1 Cohort 1

The first cohort will consist of a minimum of three patients who will receive an oral dose of 5 mg of RAD001 administered daily and an oral dose of temozolomide of 150 mg/m² daily for

7 days every other week beginning on Day 1 of RAD001 administration. The patients will be treated for a 28-day Treatment Period and then observed over a 7-day observation period for signs of treatment-emergent toxicity. Patients will not receive treatment with either RAD001 or temozolomide during the 7-day observation period. If these patients do not exhibit disease progression or a dose limiting toxicity (DLT), as defined in section 3.3, they will receive subsequent 28-day cycles of treatment without additional 7-day observation periods. Patients in this cohort may be treated simultaneously without requiring previously enrolled patients to complete their first cycle of treatment and observation.

If a dose limiting toxicity (DLT), as defined in section 3.3, is observed in 1 of the first 3 patients, 3 additional patients will be enrolled at that same dose level. If no additional DLT is observed after all patients have completed the first cycle of treatment and 7-day observation period, the trial will continue to enroll the second cohort of patients.

If a DLT is observed in 2 or more of the first 3 patients or of the total 6 patients during Cycle 1 of treatment, accrual to the trial will be suspended pending review of the events and revision of the protocol.

3.2.2 Cohort 2

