Once the first cohort of patients completes the initial 35-day cycle without experiencing a DLT, the second cohort of patients will begin enrollment. The second patient cohort will consist of at least 3 patients who will receive an oral dose of 10 mg of RAD001 administered daily and an oral dose of temozolomide of 150 mg/m² daily for 7 days every other week beginning on Day 1 of RAD001 administration. The patients will be treated for a 28-day Treatment Period and then observed over a 7-day observation period for signs of treatment-emergent toxicity. Patients will not receive treatment with either RAD001 or temozolomide during the 7-day observation period. If patients do not exhibit disease progression or a dose limiting toxicity (DLT), as defined in section 3.3, they will receive subsequent 28-day cycles of treatment without additional 7-day observation periods. Patients in this cohort may be treated simultaneously without requiring previously enrolled patients to complete their first cycle of treatment and observation.

If a DLT is observed in 1 of the first 3 patients, 3 additional patients will be enrolled at that same dose level. If no additional DLT is observed after all patients have completed the first cycle of treatment and observation period, the trial will continue to enroll the third cohort of patients. If additional DLTs are observed, enrollment to the trial will be stopped and the study will be re-evaluated.

If a DLT is observed in 2 or more of the first 3 patients or of the total 6 patients during Cycle 1 of treatment, accrual to the trial will be suspended pending review of the events and revision of the protocol.

3.2.3 Cohort 3

Once the second cohort of patients completes the initial 35-day cycle without experiencing a DLT, the third cohort of patients will begin enrollment. The third patient cohort will consist of 32 patients who will receive an oral dose of the maximum tolerated dose of RAD001 administered daily and an oral dose of temozolomide of 150 mg/m² daily for 7 days every other week beginning on Day 1 of RAD001 administration. The patients will be treated for a 28-day Treatment Period. Patients who complete the initial cycle of therapy without evidence of significant treatment-emergent toxicity or progressive disease may receive additional 28-day cycles of treatment until the appearance of significant treatment-emergent toxicities or disease progression.

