3.3 Definition of dose limiting toxicity (DLT) and maximum tolerated dose (MTD)

Dose limiting toxicity is defined as drug-related toxicity according to the NCI CTCAE v3.0 during the first cycle of treatment leading to the following:

- Grade 3 or higher non-hematologic toxicity (excluding nausea and/or vomiting).
- Grade 3 or higher nausea/vomiting uncontrolled by aggressive antiemetic support.
- Grade 3 or higher neutropenia or thrombocytopenia failing to revert to grade ≤ 2 (level at which cytotoxic treatment is permitted) in three weeks
- Febrile neutropenia
- Inability of the patient to take $> 75\%$ of the planned chemotherapy dose during the treatment period.
- Clinically significant treatment related toxicity

The maximum tolerated dose (MTD) is defined as the highest dose level at which less than 33% of the patients experience a DLT.

If a DLT is observed in 2 or more of the first 3 patients or of the total 6 patients in a dose level during cycle 1 of treatment, that dose level will be considered to be above the maximum tolerated dose (MTD). The dose one level lower will be declared as the MTD, if a DLT is observed in 1 or less patient of the total 6 patients in the dose level. If 2 or more patients have experienced a DLT at the first dose level, the investigator, medical monitor, and Sponsor may discuss to add a dose level at 50% of the first level.

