4.3 Monitoring of suspected toxicities

Patients whose treatment is interrupted or permanently discontinued due to an adverse event or abnormal laboratory value suspected to be related to RAD001 or temozolomide must be followed at least weekly until the adverse event or abnormal laboratory resolves or returns to grade 1. If a patient requires a dose delay of > 21 days from the intended day of the next scheduled dose, then the patient must be discontinued from the study.

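### The next cohort may open at Day 35 while a late first-cycle Grade ≥3 neutropenia or thrombocytopenia is still unseen, or undecided under the three-week DLT criterion

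*Combined protocol and SAP*

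**What the plan says.** **Opening the next cohort.** In Cohorts 1 and 2, cycle 1 is 28 days of treatment plus 7 days of observation off drug. Section 3.2.2 says "Once the first cohort of patients completes the initial 35-day cycle without experiencing a DLT, the second cohort of patients will begin enrollment". Section 3.2.3 repeats the rule: "Once the second cohort of patients completes the initial 35-day cycle without experiencing a DLT, the third cohort of patients will begin enrollment". Where one DLT has expanded a cohort to six, section 3.2.1 continues "If no additional DLT is observed after all patients have completed the first cycle of treatment and 7-day observation period", and section 3.2.2 has a near-identical sentence. Within Cohorts 1 and 2, "Patients in this cohort may be treated simultaneously without requiring previously enrolled patients to complete their first cycle of treatment and observation".

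**DLT definition (section 3.3).** The toxicity must be drug-related and occur in the first cycle. The criterion for blood counts is "Grade 3 or higher neutropenia or thrombocytopenia failing to revert to grade ≤ 2 (level at which cytotoxic treatment is permitted) in three weeks". Other routes are febrile neutropenia, inability to take more than 75% "of the planned chemotherapy dose during the treatment period", and "Clinically significant treatment related toxicity".

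**Blood counts.** Sections 5.1.2.1 and 5.1.2.2 and Table 5.1 schedule a CBC on Day 1 of each cycle and on Day 15 of cycles 1 to 6. Section 7 allows ±2 days. Under section 4.3, patients whose treatment is interrupted or stopped for a suspected toxicity "must be followed at least weekly until the adverse event or abnormal laboratory resolves or returns to grade 1". Section 4.4.3 requires weekly CBCs, for up to three weeks, when a dose cannot be given on its scheduled day.

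**The concern.** The decision to open a cohort and the criterion that feeds it run on different clocks. The decision falls at Day 35, but the criterion needs three weeks from onset. A cytopenia that begins late in cycle 1 can be unresolved at Day 35 without yet being a DLT, and no sentence makes enrollment wait for it. The visit schedule adds a second gap, because the observation week carries no required blood count and such an event may not have been seen at all.

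The escalation steps are at stake. With no confirmed DLT in three patients, one pending event means the expansion to six that 1/3 requires does not happen. With one confirmed in six, one pending event lets the next cohort open where 2/6 would suspend accrual. New patients could then start RAD001 10 mg in Cohort 2, or enter the 32-patient Cohort 3, before the earlier result is known.

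The protocol gives its own reasons for care. Section 1.3.2.1 says some patients may be especially sensitive to RAD001 myelosuppression and calls for careful count monitoring when treatment starts. It also reports DLTs in 5 of 8 patients on RAD001 plus gemcitabine, attributed in part to possible delay in marrow recovery. The paclitaxel combination, by contrast, had none in 16.

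**Working it through.** **Inputs.** Cycle 1 is 28 + 7 = 35 days (sections 3.2.1 and 3.2.2), which reproduces the plan's figure. The recovery period is 21 days (section 3.3). Temozolomide is given on Days 1-7 and 15-21, or 14 doses (section 4.4.2). RAD001 is given daily, or 28 doses. CBCs fall on Day 1, Day 15 and cycle 2 Day 1.

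**Step 1: latest onset that can be settled by Day 35.** Onset on Day d is settled on Day d + 21, so d ≤ 35 − 21 = 14. If the onset day is counted as the first of the 21, the limit moves by one day, to Day 15.

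**Step 2: what the dose criterion catches.** Suppose the event is detected, both drugs are held from Day d, and dosing is not resumed.

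- Temozolomide taken is [7 + (d − 15)]/14 for holds in the second dosing week: Day 15, 7/14 = 50.0%; Day 16, 8/14 = 57.1%; Day 17, 9/14 = 64.3%; Day 18, 10/14 = 71.4%; Day 19, 11/14 = 78.6%. Holds up to Day 18 are already DLTs; from Day 19 they are not.
- RAD001 taken is (d − 1)/28: Day 22, 21/28 = 75.0%, which is not above 75%; Day 23, 22/28 = 78.6%. If RAD001 counts by itself, the open window starts at Day 23.
- Pooling the dosing days of both drugs (14 + 28 = 42) gives Day 21: (13 + 20)/42 = 78.6%.

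If the event is not detected, dosing is not held for it, this criterion does not act, and the window starts at Day 15.

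**Step 3: how long the status stays open.** Days after Day 35 = d + 21 − 35 = d − 14.

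| Onset | Settled | Days after Day 35 |
|---|---|---|
| Day 15 | Day 36 | 1 |
| Day 19 | Day 40 | 5 |
| Day 23 | Day 44 | 9 |
| Day 28 | Day 49 | 14 |
| Day 35 | Day 56 | 21 |

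**Step 4: would the event be seen?** Cycle 2 Day 1 is 28 + 7 + 1 = Day 36, or Days 34-38 with the visit window. The gap between scheduled counts is 36 − 15 = 21 days (34 − 17 = 17 to 38 − 13 = 25 with the windows). The weekly checks in sections 4.3 and 4.4.3 follow an event already acted on; they do not find one. No drug is scheduled on Days 29-35, so a missed dose cannot trigger them in that week. An event first seen on Day 36 has no known onset date, so the table cannot be applied to it directly.

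**Context only.** The attached temozolomide label gives median nadirs at Day 26 (platelets) and Day 28 (neutrophils), inside the gap between counts. It reports Grade 3-4 platelets in 29/156 (19%) and neutrophils in 20/142 (14%). Those figures come from a 5-day schedule. The label also advises a Day 22 CBC, which Table 5.1 does not adopt.

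**The case against.** **Silence is not permission.** A patient with a known, open Grade ≥3 cytopenia has arguably not been shown to be free of a DLT, and a careful investigator would wait. The last route in section 3.3 also allows an early DLT call, and febrile neutropenia counts at once. This stands as a description of good conduct. It is discretionary, however, and does nothing for an event that nobody has seen. The DSMC (section 12.2) meets quarterly or more often if required, and its review is not a condition for opening a cohort.

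**Late events still count.** A reader might infer that these events drop out and that the MTD will be set too high. The documents do not support that. Section 3.3 ties the toxicity to the first cycle, and its natural reading includes a cycle 1 cytopenia confirmed after Day 35. The rule on two or more DLTs would still apply then.

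**Day 19 is not a settled threshold.** This is correct. It depends on reading chemotherapy as temozolomide alone, and on the event being detected and held. Once an event is held, weekly follow-up applies and its open status is known at Day 35.

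**The overlap may be small in practice.** The Day 36 count nominally comes one day after the decision point, and registration must precede dosing (sections 11.1 and 11.2). In the earlier thalidomide study on this same temozolomide schedule (section 1.2), Grade 3-4 neutropenia occurred in 2 of 29 patients (6.9%), over a median of 7.3 months. The label puts average recovery to normal within 14 days of nadir. Three new starts within the overlap is speculative in a disease with an incidence of 3.5 to 4 per million. These points make the problem less likely; they do not close it.

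**Dose steps are limited.** Temozolomide is 150 mg/m² throughout, and Cohort 3 is treated at the declared MTD. The added exposure is therefore chiefly the move from RAD001 5 mg to 10 mg.

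**Conclusion.** The point holds as a gap in the opening rule and the visit schedule. Followed exactly as written, the plan lets new patients start before a late first-cycle cytopenia has been detected or classified. The status can stay open for up to 21 days after Day 35. The window starts at Day 15 for undetected events; for detected and held events it starts at Day 19 or Day 23, depending on what chemotherapy means in section 3.3.

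The consequence is avoidable exposure during that period, with an expansion or suspension step possibly skipped until the event is confirmed. A wrong MTD does not follow unless late-confirmed events were ignored, which section 3.3 does not suggest. Neither the number of patients exposed nor the frequency can be computed: no accrual rate is given, and neither the label nor the earlier study shows how many events would be open at Day 35 or last three weeks. A pending event must be Grade ≥3, start late, be afebrile and not be called clinically significant. It must also last 21 days to become a DLT by this route, so the frequency is probably low. The change is worth making because it protects patients at little cost.

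**What to change.** 1. In sections 3.2.1 to 3.2.3, open the next cohort only when every patient's cycle 1 DLT status is settled. Follow any Grade ≥3 neutropenia or thrombocytopenia open at Day 35 with weekly CBCs until grade ≤2, or until three weeks from the first documented Grade ≥3 count. That starting point is needed because true onset may not be datable.
2. In section 5.1.2 and Table 5.1, for cycle 1 of Cohorts 1 and 2, require a CBC at the end of the observation period and review the result before the next cohort opens. A further CBC around Day 22, as the attached label advises, would help date onset.
3. As a clarification in section 3.3, state that a cytopenia first documented in cycle 1 counts even if its three weeks end after Day 35.

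**Cost.** Protocol wording, and one or two routine CBCs in 6 (3 + 3) to 12 (6 + 6) patients. There is a wait of up to 21 days, to Day 56 at the latest, only when such an event is open. If cycle 2 is delayed on Day 36, the weekly CBCs in section 4.4.3 can already run to Day 57 (36 + 21), so that follow-up needs no extra visits.

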4.1 Study Treatment

The investigational study drugs used in the course of this trial are RAD001 and temozolomide:

- Cohort 1: Patients will receive an oral dose of 5 mg of RAD001 administered daily and an oral dose of temozolomide of 150 mg/m² daily for 7 days every other week beginning on Day 1 of RAD001 administration. Temozolomide will be administered for a maximum of 6 months; RAD001 may be administered until treatment progression, unacceptable or dose limiting toxicity, withdrawal of consent, or other reason for treatment discontinuation.
- Cohort 2: Patients will receive an oral dose of 10 mg of RAD001 administered daily and an oral dose of temozolomide of 150 mg/m² daily for 7 days every other week beginning on Day 1 of RAD001 administration. Temozolomide will be administered for a maximum of 6 months; RAD001 may be administered until treatment progression, unacceptable toxicity, withdrawal of consent, or other reason for treatment discontinuation.
- Cohort 3: Patients will receive an oral dose of RAD001 administered daily at the MTD as established in the phase I component of the study (Cohorts 1 and 2) and an oral dose of temozolomide of 150 mg/m² daily for 7 days every other week beginning on Day 1 of RAD001 administration. Temozolomide will be administered for a maximum of 6 months; RAD001 may be administered until treatment progression, unacceptable toxicity, withdrawal of consent, or other reason for treatment discontinuation.

Patients on study therapy may be at risk for temozolomide-related selective lymphopenia and opportunistic infections. To reduce the risk of opportunistic infections, patients will receive prophylaxis with Bactrim DS, 1 tablet by mouth every Monday, Wednesday, and Friday beginning after the first month of treatment. Patients allergic to Bactrim should be initiated on an alternate, standard PCP prophylaxis regimen. Previous infections associated with temozolomide-induced lymphopenia in neuroendocrine tumor patients have developed after more than 6 months of treatment. Treatment with temozolomide in this study will therefore be limited to a maximum duration of 6 months.

Novartis will supply RAD001, and Schering-Plough will provide temozolomide free of charge for study participants.

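### Does section 3.3 leave the MTD undecided when Cohort 1 closed with no DLT in 3 patients and Cohort 2 then shows 2 or more?

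*Combined protocol and SAP*

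**What the plan says.** Section 3.2.1 sets the size of the first level: "The first cohort will consist of a minimum of three patients". The only written trigger for 3 more patients is 1 DLT among the first 3. With no DLT, Cohort 2 opens, so Cohort 1 can close at 0/3.

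Section 3.3 then contains two statements about the MTD. The general one is "defined as the highest dose level at which less than 33% of the patients experience a DLT", with no minimum number of patients. The other applies once a level has shown 2 or more DLTs: the level below is to be "declared as the MTD, if a DLT is observed in 1 or less patient of the total 6 patients in the dose level".

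Section 3.2.2 says what happens to the trial when Cohort 2 has 2 or more DLTs. For a further DLT after expansion it reads: "If additional DLTs are observed, enrollment to the trial will be stopped and the study will be re-evaluated". For 2 or more among the first 3, or among the 6, "accrual to the trial will be suspended pending review of the events and revision of the protocol". After exactly 1 DLT in 6, "the trial will continue to enroll the third cohort of patients". Section 3.2.3 nevertheless begins: "Once the second cohort of patients completes the initial 35-day cycle without experiencing a DLT, the third cohort of patients will begin enrollment". Sections 3.2.3 and 4.1 give Cohort 3 the MTD found in the first two cohorts.

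**The concern.** Suppose Cohort 1 closes at 0/3 and Cohort 2 then has 2 or more DLTs. The percentage definition is met at the lower level (0%). The declaration sentence refers to 6 patients, of whom only 3 exist, and nothing instructs the team to enrol the rest. Section 3.3 therefore seems to give two answers to one question, and it does not say how its declaration relates to the halt in 3.2.2.

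The MTD is the RAD001 dose for the 32 patients of Cohort 3. If a rule that looks fixed in advance can be read two ways, the choice between 3 and 6 patients would be made after the DLT data are known.

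A smaller mismatch sits beside it. The opening sentence of 3.2.3, read literally, admits no DLT at all, although 3.2.2 continues after 1 in 6. The opening of 3.2.2 does the same to 3.2.1, and sections 1.5 and 10.1 describe only the route without toxicity.

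**Working it through.** **1. The plan's own counts.** Section 10.1 allows at most 12 patients in Cohorts 1 and 2 and 32 in Cohort 3. Two levels of 6 give 6 + 6 = 12, and 12 + 32 = 44, the stated total. A Cohort 1 of 3, a Cohort 2 of 6 and 3 more at the lower level also make 3 + 6 + 3 = 12. The ceiling leaves room for 6 at the lower level but does not order it.

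**2. Every route through the rules.**

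| Cohort 1 closes at | Cohort 2 shows | Effect under 3.2 | MTD under 3.3 |
|---|---|---|---|
| 0/3 or 1/6 | 0/3 | Cohort 3 opens | Cohort 2 level (0%, below 33%) |
| 0/3 or 1/6 | 1/6 | Cohort 3 opens | Cohort 2 level (16.7%, below 33%) |
| 1/6 | 2 or more | Accrual halted, review or revision | Cohort 1 level meets both statements (16.7%; 1 of 6) |
| 0/3 | 2 or more | Accrual halted, review or revision | Percentage definition met (0%); 6-patient condition cannot yet be tested |

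Only the last row is open, and there the trial is already halted. On the two rows that lead directly to Cohort 3, the sentence about the lower level is never invoked.

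**3. How often the last row occurs.** The documents give no DLT rates, so the rates here are assumptions: q2 in Cohort 2 and q1 in Cohort 1.

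- P(2 or more DLTs in Cohort 2) = 1 − (1 − q2)³ − 3q2(1 − q2)⁵. For q2 = 0.10, 0.20, 0.33 this is 0.094, 0.291, 0.566.
- P(Cohort 1 closed at 0/3, given that Cohort 2 opens) = (1 − q1)³ / [(1 − q1)³ + 3q1(1 − q1)⁵]. With q1 = q2/2 = 0.05, 0.10, 0.165 this is 0.881, 0.805, 0.743. With q1 = q2 it is 0.805, 0.723, 0.692.
- The product is 0.083, 0.234, 0.420 for q1 = q2/2, and 0.076, 0.211, 0.392 for q1 = q2.

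These are the chances of a halt after a 0/3 Cohort 1. They are not chances of a wrong dose.

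**4. How often the two readings would end differently.** If 3 patients were added after 0/3, the 6-patient condition would fail only with 2 or more DLTs among them. That probability is 3q1²(1 − q1) + q1³.

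| Assumed q2 | q1 | Halt after 0/3 | 2 or more in 3 added | Product |
|---|---|---|---|---|
| 0.10 | 0.05 | 0.083 | 0.007 | 0.06% |
| 0.20 | 0.10 | 0.234 | 0.028 | 0.7% |
| 0.33 | 0.165 | 0.420 | 0.073 | 3% |
| 0.10 | 0.10 | 0.076 | 0.028 | 0.2% |
| 0.20 | 0.20 | 0.211 | 0.104 | 2% |
| 0.33 | 0.33 | 0.392 | 0.255 | 10% |

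**5. What each count shows.** The exact one-sided 95% upper limit on the DLT rate is 1 − 0.05^(1/3) = 63% after 0/3, 58% after 1/6, and 1 − 0.05^(1/6) = 39% after 0/6. Both statements in 3.3 accept 1/6, whose limit is close to that of 0/3. This comparison does not choose between the readings.

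**The case for a change.** The best argument for a change is that the halt does not answer the question. Section 3.2.2 asks for review and revision, section 3.3 speaks as though the lower level's status is settled by rule, and no sentence puts the two in order. The branch is not rare: 0/3 is the commonest way to pass Cohort 1, and under the assumed rates the halt follows it in 8%, 23% or 42% of trials that reach Cohort 2. A short decision table would cost no patients beyond the 12 already allowed.

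Part of this stands. The step from 3 to 6 patients at the lower level is not written, and neither is the order of halt and declaration. But a definition and a stricter condition for declaring can both hold: the declaration sentence does not reject 0/3, it is simply not yet satisfied. The 8%, 23% and 42% mostly count a stop that the plan intends. Deciding the next step after the DLTs have been seen is what 3.2.2 openly prescribes, and section 8 sends any amendment to the IRB. A table written now would have to leave its content to the sponsor, and on this branch the protocol is due for revision anyway.

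**Conclusion.** This is a missing step on a branch that already ends in a halt and a protocol revision. Every route to Cohort 3 that needs no amendment yields a clear MTD. Followed exactly as written, the plan enrols nobody in Cohort 3 under the unclear wording, and the two-stage rule for the 32 patients and its error rates do not depend on it.

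The readings would end in different answers in about 0.06% to 3% of trials that reach Cohort 2 when Cohort 1 has half the Cohort 2 DLT rate, and in 0.2% to 10% when the rates are equal. These figures rest wholly on assumed rates of 10% to 33% in Cohort 2. Even then, the difference would arise within the review, before any Cohort 3 dose is set.

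The zero-DLT wording that opens 3.2.2 and 3.2.3 is a clerical slip, because 3.2.1 and 3.2.2 state the 1-in-6 continuation expressly. If the branch occurs, sections 3.2.2 and 3.3 must be reconciled in the revision that 3.2.2 requires, and which clinical rule applies is for the sponsor. No separate change is needed.
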